		3. Safety disclosure section with two tables related to adverse events (non-serious AE and death due to SAE) are added in order to comply with legal requirements pertinent to the disclosure of study results (Section 5.10.1)

1 Introduction

This document describes the detailed statistical methodology of the Report Analysis Plan (RAP) of Study SOM230C1202 required for reporting the results of final clinical study report (CSR).

The first analysis, for the purpose of the First Interpretable Results (FIR) only, was conducted when the last patient completed the Month 3 assessment with data cut-off date on 31-Jul-2014. The second analysis was conducted, when the last patient completed the Month 12 assessments (with data cut-off date on 2-Apr-2015), and the results were reported in an interim CSR dated 01-Jul-2015. Details on the final analysis are provided in the Section 4.2 for final CSR. For completeness a short description of prior analysis is provided in the same section.

[figure not shown]
Data will be analyzed by Novartis personnel or a designated third party. This RAP contains relevant statistical considerations for the final analysis which will contain cumulative data generated from first patient first visit (FPFV) to last patient last visit (LPLV) until all patients have withdrawn study. Further supportive statistical information will be provided in the [Appendix 16.1.9 of the CSR].

2 Study design

A total of 33 eligible patients were enrolled and randomized to one of 3 doses of pasireotide LAR (20 mg, 40 mg, or 60 mg) in a ratio of 1:1:1. Randomization was stratified by prior medications (e.g. somatostatin analogues or dopamine agonists), (yes or no). Intramuscular administration of pasireotide LAR has been repeated every month (1 month = 28 days) for 12 months in core phase. It is permitted to increase the dose up to 60 mg in a patient showing the following biochemical test results after 3 and 6 months of study treatment: mean GH levels $\geq 2.5 \,\mu\text{g/L}$ and/or IGF-1 > ULN (age and sex related). In the event of any problem with tolerability, it is permitted to reduce the next lower dosage level at any time. After 3 months of study treatment, the primary endpoint (proportion of patients with a reduction of mean GH levels to $\leq 2.5 \,\mu\text{g/L}$ and normalization of IGF-1 to within normal limits) will be evaluated.

Patients with a reduction of mean GH levels to <2.5 μ g/L and normalization of IGF-1 at the end of the 12-month study treatment will be enrolled in an extension phase of study treatment. Patients with a mean GH level $\geq 2.5 \mu$ g/L and/or IGF-1 > ULN at the end of the 12- month study treatment may be enrolled in an extension phase of study treatment if the extended study treatment is thought to be clinically beneficial for them by the investigator. Patients will receive pasireotide LAR in the extension phase until unacceptable toxicity appears or until the medication is commercially available or until the pasireotide LAR development program is discontinued whichever comes first.

Figure 2-1 Study design

3 Objectives

Table 3-1 Objectives and related endpoints

Objective	Endpoint
Primary	
Assess the total-group efficacy of pasireotide LAR on the reduction of mean GH levels to < 2.5 μg/L and the normalization of IGF-1 at 3 months of study treatment	Proportion of patients with a reduction of mean GH levels to < 2.5 μg/L and the normalization of IGF-1 to within normal limits (age and sex related) at 3 months across all doses
Key secondary	
Assess the effect of each starting dose pasireotide LAR on the reduction of mean GH levels to < $2.5 \mu g/L$ and the normalization of IGF-1 at 3 months of study treatment	Proportion of patients with a reduction of mean GH levels to < 2.5 μg/L and the normalization of IGF-1 to within normal limits (age and sex related) at 3 months in each starting dose
Assess the PK and PK/PD of pasireotide LAR 20 mg, 40 mg and 60 mg	PK: C _{trough} , C _{max, 3rd inj} , accumulation ratio (AR) PD: GH, IGF-1
Assess the tolerability and safety profile of pasireotide LAR at 3 months and during and after the 12- month study treatment	Toxicity will be assessed using the National Cancer Institute-Common Toxicology Criteria (NCI-CTC) grading scale for Adverse Events and for laboratory assessments that include biochemistry and hematology; special safety assessments that include the regular monitoring and recording of blood glucose, HbA1c, thyroid and liver function tests, gallbladder examinations and ECGs.
Assess the effect of pasireotide LAR on the reduction of mean GH levels to < 2.5 μg/L at 3 months of study treatment	Proportion of patients with a reduction of mean GH levels to < 2.5 μg/L at 3 months

Objective	Endpoint
Assess the effect of pasireotide LAR on the normalization of IGF-1 at 3 months of study treatment	Proportion of patients with the normalization of IGF-1 to within normal limits (age and sex related) at 3 months
Other secondary (Core phase)	
Assess the effect of pasireotide LAR on the reduction of mean GH levels to < 2.5 μ g/L and the normalization of IGF-1 at 6, 9 and 12 months of study treatment	Proportion of patients with a reduction of mean GH levels to < 2.5 μ g/L and the normalization of IGF-1 to within normal limits (age and sex related) at 6, 9 and 12 months
Assess the effect of pasireotide LAR on the reduction of mean GH levels to < 2.5 µg/L at 6, 9and 12 months of study treatment	Proportion of patients with a reduction of mean GH levels to < 2.5 μ g/L at 6, 9 and 12 months
Assess the effect of pasireotide LAR on the normalization of IGF-1 at 6, 9 and 12 months of study treatment	Proportion of patients with the normalization of IGF-1 to within normal limits (age and sex related) at 6, 9 and 12 months
Assess the effect of pasireotide LAR on the change of tumor volume at 6and 12 months of study treatment	Change of tumor volume from baseline at 6 and 12 months
Assess the effect of pasireotide LAR on the change of mean GH level from baseline	Change of mean GH levels from baseline
Assess the effect of pasireotide LAR on the symptoms of acromegaly, specifically: ring size, headache, fatigue, perspiration, paresthesias, osteoarthralgia	Change of clinical signs from baseline: ring size, headache, fatigue, perspiration, paresthesias, osteoarthralgia
Assess the effect of pasireotide LAR on the change of prolactin (PRL) level from baseline	Change PRL level from baseline
Other secondary (Extension phase)	
Assess the effect of pasireotide LAR as long term study treatment on the proportion of patients with a reduction of mean GH level to < 2.5 µg/L and normalization of IGF-1 at 18 and 24 months of study treatment	Proportion of patients with a reduction of mean GH levels to < 2.5 μ g/L and the normalization of IGF-1 to within normal limits (age and sex related) a18 and 24 months of study treatment
Assess the effect of pasireotide LAR as long term study treatment on the reduction of mean GH levels to < 2.5 μ g/L at 18 and 24 months of study treatment	Proportion of patients with a reduction of mean GH levels to < 2.5µg/L at 18 and 24 months of study treatment
Assess the effect of pasireotide LAR as long term study treatment on the normalization of IGF-1 at 18 and 24 months of study treatment	Proportion of patients with the normalization of IGF-1 to within normal limits (age and sex related) at 18 and 24 months of study treatment
Assess the effect of pasireotide LAR as long term study treatment on the change of mean GH levels from baseline	Change of mean GH levels from baseline in extension phase
Assess the safety and tolerability of pasireotide LAR in extension phase	Toxicity in extension phase will be assessed using the National Cancer Institute-Common Toxicology Criteria (NCI-CTC) grading scale for Adverse Events
Assess the total-group safety and tolerability of pasireotide LAR as long term study treatment	Toxicity in total-group study treatment will be assessed using the National Cancer Institute-Common Toxicology Criteria (NCI-CTC) grading

Objective	Endpoint		
	scale for Adverse Events and for laboratory assessments that include biochemistry, hematology, urinalysis; special safety assessments that include the regular monitoring and recording of blood glucose, HbA1c, thyroid and liver function tests, gallbladder examinations and ECGs.		
	· ·		

4 Definitions and general methodology

4.1 Definitions

4.1.1 Study drug and study treatment

Study drug will refer to SOM230 (pasireotide) LAR.

4.1.2 Date of first administration of study drug

The date of first administration of study drug will be derived as the first date when a nonzero dose of study drug is administered and recorded on the dose administration record (DAR) page of the electronic case report form (eCRF). For the sake of simplicity, the date of first administration of study drug will also be referred as start date of study drug.

4.1.3 Date of last administration of study drug

The date of last administration of study drug will be defined as the last date when a nonzero dose of study drug is administered and recorded on DAR page of the eCRF. This date will also be referred as last date of study drug.

4.1.4 Study day

The study day for all assessments (i.e. efficacy, safety) will be calculated as the difference between the date of the event (i.e. visit date, onset date of an event, assessment date) and the first date of study drug plus 1. For patients who got randomized but never dosed, study day is calculated as the difference between the date of event and the date of randomization plus 1.

For any assessment or event such as baseline disease characteristics or medical history that is supposed to occur prior to the start of study drug, the study day will be negative and calculated as the difference between the date of the event and the first date of study drug.

The study day will be displayed in the data listings.

4.1.5 Baseline

The baseline will be the last pre-treatment evaluation result within 28 days of the start date of study drug.

4.1.6 On-treatment assessment/event

Safety summaries and selected summaries of deaths will be presented using only on-treatment assessments/events.

For patients who discontinue study drug, on-treatment assessment/event will be any assessment/event obtained in the time interval between start date of study drug and last date of study drug + 56 days.

4.1.7 Month

A month will be calculated as 28 days. If duration in months has to be reported, duration in days will be divided by 28.

4.1.8 Standardized IGF-1

IGF-1 normal range is age and gender dependent. When pooling all the data for analyses, unless otherwise specified, the standardized IGF-1 will be used. The standardized IGF-1 is defined as:

Standardized IGF-1 = IGF-1 value / ULN,

where ULN is the upper limit of the normal range.

4.1.9 Handling of missing values/censoring/discontinuations

If the GH and/or IGF-1 samples are taken after 35 days (=28 + 7 days) from the date of LAR injection, the values if GH and/or IGF-1 at the corresponding visit will be treated as missing. In addition, if a patient has less than 3 samples for the assessment of 5-point mean GH levels from the 2-hour profile, the mean GH levels will be considered as missing.

The patients with missing values of mean GH levels and/or IGF-1 at 3 months of study treatment or who discontinue prior to the assessment at 3 months of study treatment will be considered as non-responders.

4.1.10 Evaluation time window

GH and IGF-1 measurements taken within 35 days after the date of LAR injection are allowed and the last values of 5-point mean GH and IGF-1 within window will be used as the value of the corresponding month. For assessments beyond 3 months of study treatment, the ongoing patients will be counted in the denominator of calculation of response rate, if they have reached at each visit (e.g. Assessments collected at end of the study treatment of Core Phase will be treated at those at 12 months of study treatment as long as those were collected within the time window specified in the above). Discontinued patients are included in the denominator of calculation of response rate in the core phase and are included at a visit to which a patient reached in the extension phase.

MRI collected within +/- 35 days from the date of visit is allowed. For corresponding visit, the patient will be counted at a specific visit if they have reached at each visit.

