6.4.3 Prohibited concomitant therapy

For patients with medication naïve acromegaly or pituitary gigantism the single dose of short acting octreotide or short-acting dopamine agonists should not be administered within 3 days prior to Visit2 (baseline). In case of a single dose of short-acting octreotide, the dose should not be used to predict the response to the octreotide treatment.

The use of the following treatments is prohibited after start of study.

- Other investigational drug or therapy.
- Medication known to affect GH or IGF-1 concentration should not be taken during this study.

The use of concomitant medications with a known risk for QT prolongation is prohibited and requires the discontinuation of the patient from the study prior to starting the respective QT prolonging medication. Please refer to [Appendix 2](#) for guidance regarding medications which pose a known risk for QT prolongation.

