7.1.3.1 Criteria for premature patient withdrawal

Patients may voluntarily withdraw from the study or be dropped from it at the discretion of the investigator at any time. Patients may be withdrawn from the study if any of the following occur:

- Adverse event(s) [including abnormal laboratory value(s) and abnormal test procedure result(s)]
- Protocol deviation (including but not limited to, new therapy for acromegaly, and discovery of patient ineligibility)
- Patient withdrew consent

- Lost to follow-up
- Administrative problems
- Death
- Disease progression
- Pregnancy
- Treatment duration completed as per protocol

The investigator must also inform the premature withdrawal to Novartis, if this occurs during the core period.

In addition to the general withdrawal criteria, the following **study specific criteria** will also require study treatment discontinuation:

- Patients experiencing unacceptable toxicity, as described in [Table 6-2](#), [Table 6-3](#).
- Patients unable to tolerate the lowest dose (20 mg) as per [Section 6.3](#).
- Patients with > 28 consecutive days of treatment interruption (either due to tolerability, investigator decision or patient compliance)
- Uncontrolled diabetes mellitus, consistently high glucose values FPG \geq 240 mg/dL (13.3 mmol/L) or HbA1c value \geq 10 % despite prior appropriate management and prior dose adjustment of the study drug,
- Patients experiencing adverse events in QTc:
 - a confirmed QTcF $>$ 470msec and discontinuation recommended by a cardiologist, or
 - Mean QTcF $>$ 500 msec measured by triplicate ECGs
 - Significant arrhythmia findings from Holter monitoring such as:
 1. Any ventricular or supra-ventricular tachyarrhythmia associated with symptoms of hemodynamic compromise
 2. Sustained ventricular tachycardia ($>$ 30 sec) irrespective of symptoms
 3. Recurrent non-sustained ventricular tachycardia (\geq 3 beats) during any 24-hour monitoring period
 4. Torsades de Pointes
 5. Cardiac arrest
 6. Pause $>$ 5 seconds
 7. Second or third degree AV block
 - New occurrence of clinically significant/symptomatic bradycardia, or
 - Increased risk of QT prolongation by use of QT prolonging medication, or
 - Hypokalemia ($<$ 3.5 mmol/L) or hypomagnesaemia ($<$ 0.7 mmol/L) confirmed by repeat testing that is either a new finding or accompanied by vomiting or diarrhea and not corrected by treatment.
- Patients experiencing the abnormal hepatic criteria below:

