10.4.1 Variable

The primary variable is the total-group response rate defined as the proportion of patients with the reduction of mean GH levels to $< 2.5\mu\text{g/L}$ and the normalization of IGF-1 at 3 months of study treatment.

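### No rule covers a patient who starts other acromegaly therapy, stays on injections and then meets the GH or IGF-1 criteria; the gap matters mainly for the Month 18 and 24 response rates

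*SAP*

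**What the plan says.** **Response.** Protocol 10.4.1: "The primary variable is the total-group response rate defined as the proportion of patients with the reduction of mean GH levels to" below 2.5 µg/L together with normal IGF-1 at 3 months. Nothing is said about other therapy.

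**Overrides of an observed value.** SAP 4.1.9 (and Protocol 10.4.3) names two groups of non-responders: "The patients with missing values of mean GH levels and/or IGF-1 at 3 months of study treatment", and those "who discontinue prior to the assessment at 3 months of study treatment will be considered as non-responders". A value is missing if the sample is more than 35 days after an injection, or if fewer than 3 GH samples exist. The rule is written for Month 3 only.

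**Value used at each month.** SAP 4.1.10: "the last values of 5-point mean GH and IGF-1 within window will be used as the value of the corresponding month". For later visits that section adds only denominator rules. Discontinued patients stay in the core-phase denominator; in the extension they count only at visits they reached.

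**Other therapy.** Protocol 6.4.3: "Medication known to affect GH or IGF-1 concentration should not be taken during this study". No consequence is attached. For another drug class the same section does attach one: "The use of concomitant medications with a known risk for QT prolongation is prohibited and requires the discontinuation of the patient from the study". Protocol 7.1.3.1 says "Patients may be withdrawn from the study if any of the following occur", and that list includes "Protocol deviation (including but not limited to, new therapy for acromegaly, and discovery of patient ineligibility". The separate list of criteria that do require discontinuation does not contain new acromegaly therapy.

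**Analysis sets.** Efficacy is analysed on the FAS, whose only listed exclusion is missing consent (SAP 4.3). The Month 3 analysis is repeated on the PPS (Protocol 10.4.4). SAP 4.3 drops the PPS from the final analysis, while SAP 5.9.2.2 updates the combined, GH-only and IGF-1-only rates, most likely at Months 18 and 24.

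**The concern.** The protocol foresees that a patient may begin other acromegaly treatment, and it does not make discontinuation automatic. The analysis rules do not address that patient. If injections continue and samples fall in the window, the GH and IGF-1 values are scored as they stand, even though another drug, surgery or irradiation may have produced them.

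The trial compares three starting doses of one drug and pools them, so no arm shows what the other treatment contributed. Compared with scoring such a patient as a non-responder, the observed-value rule gives a rate that is equal or higher, never lower.

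The opportunity grows with time. From Month 3, uncontrolled patients on 60 mg may stay if the investigator sees clinical benefit (Protocol 6.3.1), and uncontrolled patients may enter the extension on the same kind of judgement (Protocol 4.1). The rates updated in the final report are the ones with the longest exposure and no per-protocol repeat.

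**Working it through.** **1. Trace one patient through the rules.** Suppose a patient starts a GH receptor antagonist at Month 14, keeps receiving injections and has in-window samples at Month 18 with mean GH below 2.5 µg/L and normal IGF-1.
- Missing value (SAP 4.1.9)? No.
- Discontinued? Not necessarily: Protocol 7.1.3.1 allows withdrawal but does not require it.
- Excluded from the FAS? No: consent was given.
- Value used? The in-window one (SAP 4.1.10).
- Result: responder. If only one of the two criteria is met, the patient counts in that single-marker rate.

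**2. Effect of one such patient on a rate.** Effect = 1/n, where n is the denominator at the visit.
- n = 33 (all randomized, SAP Section 2): 1/33 = 3.0 points.
- The number who reached Months 18 and 24 is not in the documents. With an assumed n of 30 the effect is 1/30 = 3.3 points; with an assumed n of 20 it is 1/20 = 5.0 points.

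**3. Month 3: the plan's own figure first.** Inputs from Protocol 10.8: expected rate 30%, drop-out 10%, N = 30, reference rate 10%, Clopper-Pearson two-sided 90% interval.
- Adjusted rate: 0.30 × (1 − 0.10) = 0.27, as stated.
- Expected responders: 0.27 × 30 = 8.1, so 8/30 = 26.7%.
- The lower limit is the 5% quantile of Beta(x, n − x + 1). At x = 8, n = 30 it is 14.0%, above 10%. The plan's statement reproduces.

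**4. How many reclassified patients would matter at Month 3?** The number k is an assumption. At N = 33 the expected count is 0.27 × 33 = 8.9, taken as 9.

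| k reclassified | N = 30, from 8 responders | Lower limit | N = 33, from 9 responders | Lower limit |
|---|---|---|---|---|
| 0 | 8 | 14.0% | 9 | 15.0% |
| 1 | 7 | 11.5% | 8 | 12.7% |
| 2 | 6 | 9.1% | 7 | 10.4% |
| 3 | 5 | 6.8% | 6 | 8.2% |

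At the expected result it takes three such patients of 33 (two of 30) to bring the lower limit below 10%. One patient decides the matter only if the observed count is exactly 7.

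**5. Where the 10% reference applies.** Only to the Month 3 total-group rate. The plan sets no such criterion for Months 6 to 24, so for those rates the effect is the shift in step 2.

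**The case against.** The strongest case on the other side has five parts.

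*The event is already controlled and visible.* The drugs are prohibited. New acromegaly therapy is a named deviation, and that wording is not limited to drugs, so surgery and irradiation are covered. The final report tabulates and lists deviations (SAP 5.2, 4.3), summarises concomitant medication and non-drug therapy by phase (SAP 5.8) and plots individual GH and IGF-1 (SAP 5.9.2.2). This stands as a reason to expect few cases and to expect a reader could find them. None of these outputs changes a response rate.

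*The primary result is protected.* A reader might infer that one such patient could overturn the Month 3 conclusion, since 6/33 gives a lower limit of 8.2% and 7/33 gives 10.4%. The documents do not support that as a likely outcome. The expected count is about 9, retention of uncontrolled 60 mg patients begins only at Month 3, and SAP 4.3 says the PPS analyses were already reported in the 12-month report. The PPS check is partial: it works only if the deviation is classed as major, and it removes the patient instead of scoring non-response.

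*No case is documented.* A reader might also infer that the reported rates are inflated. Nothing in the documents shows that. The default for uncontrolled patients on 60 mg is discontinuation unless benefit is seen.

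*A rule may exist elsewhere.* VAP Module 3 and the plan for the 12-month report are not available, so this cannot be excluded for Months 3 to 12. The final SAP, which governs Months 18 and 24, has none.

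*Observed values on an intent-to-treat set are a recognised choice.* True, but the plan does not state it as a choice, and with no comparator it answers a different question from the effect of pasireotide. A blanket rule would also overreach: permanent non-response after any single short-acting dose, or blanking all later continuous values, is hard to defend. A new definition at Months 18 and 24 alone would break the by-visit series. These points shape the fix.

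**Conclusion.** The point holds as a gap in the analysis rules. As written, a patient who starts new non-study acromegaly therapy, continues injections and then meets the criteria is a responder on the FAS, and this can only raise the rates. The exposure is mainly in the descriptive rates after Month 3, especially the Month 18 and 24 updates, where no per-protocol repeat exists. At Month 3 it is probably small.

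Each case is worth 1/n at the visit, 3.0 points if n = 33 and more if fewer patients reached it. The number of cases is not in the documents; if it is zero, so is the effect. The sample-size statement is unaffected.

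A reader might go further and conclude that surgery would be reported as drug-related tumour shrinkage in the extension. That goes too far: no MRI is done in the extension (Protocol 7.2.1.3), and the main Month 6 and 12 tumour summary has been reported.

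**What to change.** 1. Add to SAP 4.1.9: for the GH, IGF-1 and combined response rates, a patient who after the first dose has started new ongoing non-study acromegaly medication, or has had pituitary surgery or irradiation, is counted as a non-responder at that and all later visits. An isolated short-acting dose does not trigger the rule.
2. Identify cases from the Concomitant Medications/Significant Non-Drug Therapies CRF, which is collected to Month 24.
3. Report the Month 18 and 24 rates under this rule beside the observed-value rate, so that the series stays comparable with the reported Months 3 to 12.
4. State how many patients are reclassified at each visit from Month 3 to Month 24, including when the number is zero.
5. In change-from-baseline summaries, flag such patients and show the summary with and without their values after the new therapy.

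Cost: one SAP rule, one derived flag from existing data and a small amount of extra output. Response rates can only stay the same or fall slightly. The rule may also score as a non-responder someone who would have responded on pasireotide alone, which is why both rates should be shown. Whether such patients should be withdrawn is a clinical matter and is not addressed here.

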7.1.3 End of treatment visit including study completion and premature withdrawal

Patients who discontinue study treatment before visit 777 (if patient is in the core phase of the study) or visit 33 (if patient is in the extension phase of the study), should be scheduled for a visit as soon as possible, at which time all of the assessments listed for the visit 777 / 778 will be performed ([Table 7-1](#) and [Table 7-2](#)). An End of Treatment eCRF page should be completed, giving the date and reason for stopping the study treatment.

At a minimum, all patients who discontinue study treatment, including those who refuse to return for a final visit, will be contacted for safety evaluations (visit 779) during 56 days following the last dose of study treatment.

Patients who discontinue study treatment should be considered withdrawn from the study after the final visit assessments are performed or when it is clear that the patient will not return for these assessments.

If a study withdrawal occurs, or if the patient fails to return for visits, the investigator must determine the primary reason for a patient's premature withdrawal from the study and record this information on the End of Treatment eCRF page. The investigator must inform the premature withdrawal to Novartis.

For criteria for premature withdrawal refer to [Section 7.1.3.1](#).

End of treatment visit and Study completion visit for patients treated for more than 2 years (after Visit 33)

If a patient discontinues after 2 years of treatment (after Visit 33), only the assessments with an asterisk in [Table 7-2](#) need to be performed on visit 778 and visit 779.

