10.4.3 Handling of missing values/censoring/discontinuations

If the GH and/or IGF-1 samples are taken after 35 days from the date of any LAR injection, the values of GH and/or IGF-1 at the corresponding visit will be treated as missing. In addition, if a patient has less than 3 samples for the assessment of 5-point mean GH levels from the 2-hour profile, the mean GH levels will be considered as missing.

The patients with missing values of mean GH levels and/or IGF-1 at 3 months of study treatment or who discontinue prior to the assessment at 3 months of study treatment will be considered as non-responders.

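### The SAP's rule for Month 12 GH and IGF-1 values is not tied to Day 337 or the 12th injection, so its wording lets a controlled early stopper count as a Month 12 responder

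*SAP*

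**What the plan says.** SAP 4.1.10 sets the window for the hormone endpoints: "GH and IGF-1 measurements taken within 35 days after the date of LAR injection are allowed". The last value in the window stands for the corresponding month. For assessments after Month 3, "the ongoing patients will be counted in the denominator of calculation of response rate, if they have reached at each visit". An example in brackets follows in the same sentence: "Assessments collected at end of the study treatment of Core Phase will be treated at those at 12 months of study treatment". Its one proviso is that the sample falls inside the window just described. The next sentence deals with those who stopped: "Discontinued patients are included in the denominator of calculation of response rate in the core phase". In the extension phase, by contrast, they count only at visits they reached.

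Protocol 10.4.3 states the same limit as an exclusion: "If the GH and/or IGF-1 samples are taken after 35 days from the date of any LAR injection", the value is set to missing.

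Protocol 7.1.3 asks that a patient who stops before Visit 777 in the core phase be seen promptly, "at which time all of the assessments listed for the visit 777 / 778 will be performed". In Table 7-1 the Visit 777 column is the end-of-treatment visit for the core phase, placed at Day 337, and it includes the GH profile and IGF-1.

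The rule that missing or discontinued means non-responder (Protocol 10.4.3, SAP 4.1.9) names Month 3 only.

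**The concern.** The Month 12 proportions (composite, GH alone, IGF-1 alone) are meant to describe control after 12 months of treatment. Visit 777 has two uses: it is the Day 337 visit for completers and the exit visit for anyone who stops earlier. If every in-window Visit 777 sample is labelled Month 12, an exit sample taken months earlier can be carried to Month 12. A patient who stopped for a safety reason while biochemically controlled would then be a success at a visit never reached. Compared with non-responder handling, this can only leave the rate unchanged or raise it. Two programmers working from the same text could produce different Month 12 rates.

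**Working it through.** The plan gives no figure for the Month 12 rate or for core-phase discontinuation, so there is none to reproduce on this point. The nearest is the Month 3 planning rate in Protocol 10.8, which does reproduce: 0.30 × (1 − 0.10) = 0.27. It is used below only to set a scale.

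**Does an early exit sample meet the stated condition?** Table 7-1 puts injection *k* on Day 1 + 28(*k* − 1). The latest in-window day is that day + 35.

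| Last injection | Day given | Latest in-window day | Days before Day 337 |
|---|---|---|---|
| 4th (Month 3) | 85 | 120 | 217 |
| 6th (Month 5) | 141 | 176 | 161 |
| 7th (Month 6) | 169 | 204 | 133 |
| 11th (Month 10) | 281 | 316 | 21 |
| 12th (Month 11) | 309 | 344 | −7 (Day 337 is inside) |

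Only the 12th injection has a window that contains Day 337. Exit samples after the earlier injections still meet the 35-day condition, which is the only one attached to the Month 12 mapping.

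**Does another rule stop it?**
- The non-responder rule names Month 3 only.
- The ±2-day allowance for Visit 777 in Protocol 7.1.2 governs visit conduct, and the SAP's mapping does not cite it.
- The sentence on discontinued patients puts them in the denominator but does not say how they enter the numerator.

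**Size per patient.** The SAP (section 2) reports 33 randomized, so one patient is 1/33 = 3.0 points.

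**Illustration.** Assume 9 true Month 12 responders, close to the 27% planning rate. Clopper-Pearson 95% intervals:
- none added: 9/33 = 27.3% (13.3 to 45.5)
- one early stopper added: 10/33 = 30.3% (15.6 to 48.7)
- three added: 12/33 = 36.4% (20.4 to 54.9)

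**Range under assumed rates.** The shift in points is 100 × (share stopping early) × (share of those controlled at exit), taking every exit sample as in window.
- 10% stopping, 30% to 100% controlled: 3 to 10 points
- 20% stopping, 30% to 100% controlled: 6 to 20 points

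None of these shares is a Month 12 figure from the documents. The 10% matches the dropout used in the Month 3 sample-size argument. The upper ends are ceilings, because Protocol 7.1.3.1 also provides for stopping for lack of efficacy, and those patients would fail the composite however they were mapped.

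**The case against.** The strongest reply is that the mapping is an example inside a sentence whose subject is ongoing patients who have reached the visit. A patient who stops at Month 5 is neither. Discontinued patients then get their own sentence, and keeping them in the denominator after they stop most naturally means counting them as non-responders. Completers also need the rule: Visit 777 is their only Day 337 core visit, and 309 + 28 = 337 with seven days of slack fits the 35-day limit. The reference to the corresponding month points the same way, since a sample after the Month 5 injection does not obviously correspond to Month 12.

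Most of this stands. A reader might infer that the SAP instructs early exit values to be carried to Month 12, or that the Month 12 rate is biased. The documents support neither: the context suggests completers may be all that was intended, and the number of controlled early stoppers is not given.

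It does not close the gap. The bracketed text speaks of end-of-core-treatment assessments without limiting them to completers. The requirement to have reached a visit is applied to discontinued patients in the extension phase but not in the core phase. Core-phase stoppers are therefore counted at visits they did not reach, and non-responder status there is a sensible inference, not a stated rule.

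The consequence is also limited. These are descriptive secondary estimates, and SAP 5.9.2.2 says most secondary results were already in the 12-month CSR. The analysis plan for that report is not among the documents, so how Month 12 was derived there cannot be checked.

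**Conclusion.** The point holds as an ambiguity. The mapping has no anchor to Day 337 or the 12th injection, early core-phase stoppers have the same visit, and their responder status at Months 6, 9 and 12 is unstated. The wording thus permits, without requiring, a controlled early stopper to be a Month 12 responder. The size is 3.0 points per such patient on a denominator of 33, and any total rests on assumed rates. If no core-phase stopper was controlled at an in-window exit visit, the effect is zero. The Month 3 primary endpoint has its own non-responder rule and is unaffected. This is a cheap improvement, not a threat to the trial's main conclusion.

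**What to change.** In SAP 4.1.10:

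1. Map Visit 777 to Month 12 only when it falls in a stated window around Day 337 (or follows the 12th injection) and lies within 35 days of that injection.
2. State that patients who discontinue in the core phase are non-responders at all later core visits (Months 6, 9 and 12), for the composite, GH and IGF-1 rates alike.
3. Check whether any Month 12 responder already reported came from an early Visit 777, and say so in the final CSR either way.

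The cost is a sentence or two, a listing check, and a re-run if the check finds a case. The Month 12 rate could then come out slightly lower than in the 12-month CSR, which would need a short explanation.
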